## Study Summary

Title	A phase II, open-label, single arm, multicenter study of Avelumab with hypofractionated re-irradiation (HFRT) in adult subjects with transformed IDH mutant glioblastoma (GBM)
Short Title	Phase II trial of Avelumab with HFRT in adult transformed IDH mutant GBM
Protocol Number	s16-01179
Phase	Phase 2
Methodology	Multicenter, open-label, single arm, 2 stage phase II study with a safety lead-in.
Study Duration	Approximately 24 months from start of screening to last subject processed and finishing the study)
Study Center(s)	Multicenter. Four sites: 1) Perlmutter Cancer Center (PCC) at New York University Langone Medical Center (NYULMC) 2) Dana-Farber/Harvard Cancer Center (DF/HCC), which includes Massachusetts General Hospital, Dana-Farber Cancer Institute and Beth Israel Deaconness Medical Center 3) University of California, San Francisco (UCSF) 4) University of California, Los Angeles (UCLA)
Objectives	
Primary Objectives:
 
 
To assess the safety and toxicities of, and recommended phase 2 dose (RP2D) of Avelumab when administered with HFRT in adults with IDH mutant gliomas that have transformed to GBM after temozolomide or PCV chemotherapy. There will be a Safety Lead-In cohort of 6 patients followed by an expansion cohort in which the primary objective will be;
 
To estimate the 6-month progression-free survival (PFS6) of Avelumab + HFRT in adults with IDH mutant gliomas that have transformed to GBM after temozolomide or PCV chemotherapy;
 
 
Secondary Objectives:
 
 
Assess the safety, toxicities and tolerability of Avelumab + HFRT in adults with IDH mutant gliomas that have transformed to GBM after temozolomide or PCV chemotherapy;
 
Estimate the 12-month OS, median PFS, Response Rate, and median duration of response;
 
Explore the association of PFS6 with: hypermutation phenotype; proportion of predicted mutation-associated neoantigens among all somatic mutations; tumor PD-L1 expression; baseline and change in regulatory T cell (Treg) and myeloid-derived suppressor cell (MDSC) levels
 

Number of Subjects	A minimum of 12 subjects and a maximum of 61 subjects will be registered

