After screening procedures and registration, subjects will be treated with one dose of Avelumab (10 mg/kg IV) followed by hypofractionated radiotherapy (HFRT, 5 fractions of 5 Gy each fraction on consecutive days) that initiates 7 days after the first dose of Avelumab. Avelumab will continue to be given once every 2 weeks after the first dose. One treatment cycle is defined as 28 days, corresponding to 2 doses of Avelumab. Subjects will be evaluated every 8 weeks with radiographic imaging to assess response to treatment. The Immunotherapy Response Assessment for Neuro-Oncology (iRANO) criteria (**Attachment 3**), which is based on the immune-related response criteria and the RANO criteria for brain tumor response assessment, will be used as the primary efficacy endpoint of PFS. Adverse events will be monitored throughout the trial and graded in severity according to the guidelines outlined in the NCI Common Terminology Criteria for Adverse Events (CTCAE) version 4.03.

Avelumab administration will continue for 2 years or until progression of disease, unacceptable adverse event(s), intercurrent illness that prevents further administration of treatment, investigator's decision to withdraw the subject, subject withdrawal of consent, pregnancy of the subject, noncompliance with trial treatment or procedure requirements. Expected duration of subject participation is 4 months, which is the median progression-free survival for standard therapy in recurrent GBM.

End of treatment assessments will be performed within 7 days after last drug administration or within 7 days after decision to end treatment. After the end of treatment, each subject will be followed for 30 days for adverse event monitoring and 90 days for serious adverse event reporting. All subjects will be followed until resolution or stabilization of any serious or reportable adverse events occurring during treatment or starting within 30 days of last study drug. Assessments may continue for ongoing reportable adverse events. All subjects will be followed by telephone contact every 3 months or medical record review for overall survival until death.

Specific procedures to be performed during the study, as well as their prescribed times and associated visit windows, are outlined in the **Schedule of Events (Attachment 1)**.

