### **3.3 Secondary Study Endpoints**

- **Assess the safety and tolerability of Avelumab + HFRT in adults with *IDH* mutant gliomas that have transformed to GBM after temozolomide or PCV chemotherapy.**

An important secondary objective of this study is to characterize the safety, toxicities and tolerability of Avelumab when administered with HFRT among subjects with transformed *IDH* mutant GBM beyond the Safety Lead-In. A safety analysis of the phase II portion of the trial will include all subjects who experience toxicities as defined by CTCAE 4.03 criteria. Safety will be assessed by quantifying the toxicities and grades experienced by subjects who have received Avelumab with HFRT, including serious adverse events (SAEs), immune-related adverse events (irAEs) and AESIs.

Safety will be assessed by reported adverse experiences using CTCAE, Version 4.03. The attribution to drug, time-of-onset, duration of the event, its resolution, and any concomitant medications administered will be recorded. AEs will be analyzed including but not limited to all AEs, SAEs, and fatal AEs. Furthermore, irAEs and AESIs will be collected and designated as adverse events as described in **Section 3.4** and **Section 5.2.3.3**. For statistical details of the **Primary Safety Endpoint** for the phase II trial, see **Section 3.4**.

- **Estimate the 12-month OS, median PFS, Response Rate, and median duration of response.**

To further define efficacy of Avelumab + HFRT in this study population, secondary measures of efficacy will be assessed, including 12-month overall survival (OS), median progression-free survival (PFS), the radiographic response rate and median duration of response. The subjects treated at the RP2D in the Safety Lead-In will be included as a separate cohort for the evaluation of outcomes in the phase II study. See **Statistical Methods, Section 7.2**, for details of these secondary study endpoints.

CONFIDENTIAL

- **Association of PFS6 with: hypermutation phenotype; proportion of predicted mutation-associated neoantigens among all somatic mutations; tumor PD-L1 expression; baseline and change in regulatory T cell (Treg) and myeloid-derived suppressor cell (MDSC) levels.**

For complete details of laboratory correlative secondary endpoints, including background and rationale, handling/shipping of research specimens and description of the methods, see **Attachment 7** and the **Lab Manual**.

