### **4.5.2 Data Collection and Follow-up for Withdrawn Subjects**

For End of Treatment required assessments see **Section 6 (Study Procedures)**, and **Schedule of Events (Attachment 1)**. After the end of treatment, each subject will be followed for 30 days for adverse event monitoring and 90 days for serious adverse event reporting. Assessments may continue for ongoing reportable adverse events. A visit is to be performed at 30 days ( $\pm 7$  days) after the last study drug is given. Participants removed from protocol therapy for unacceptable adverse events will be following until resolution or stabilization of the adverse event.

Subjects who discontinue for reasons other than progressive disease will have post-treatment follow-up for survival. After coming off study, each subject will be contacted every 3 months by telephone or medical record review to assess survival status until they meet criteria for removal from study as detailed below.

- Withdrawal of permission to record at least survival data
- Lost to follow-up
- Death

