#### 5.2.3.7 Permanent Discontinuation of Study Treatment

In the event of an infusion reaction of Grade  $\geq 3$  severity during or directly following Avelumab infusion, dosing should be stopped and the patient must permanently discontinue Avelumab treatment.

Study treatment will be permanently stopped in the event of evidence of pregnancy.

In addition, study treatment for any subject may be discontinued for other safety reasons or compliance issues at the discretion of the investigator, overall PI or sponsor. A subject may choose to discontinue study treatment or study participation at any time for any reason.

A subject who permanently discontinues Avelumab treatment may continue follow-up in the study without additional treatment until progression of disease or closure of the study (**Section 4.5**). A patient who permanently discontinues study treatment and who does not withdraw from study participation will be asked to return to the clinic for all remaining study visits per the visit schedule (**Attachment 1**) or continue in the follow-up phase of the study until progression of disease or closure of the study (**Section 4.5.2**).

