## 6.8 Post Treatment Procedures

**Follow up post-treatment:** All participants will be followed until resolution or stabilization of any serious or reportable adverse events occurring during treatment or starting within 30 days of last study drug. After the end of treatment, each subject will be followed for 30 days for adverse event monitoring and 90 days for serious adverse event reporting. Assessments may continue for ongoing reportable adverse events. Participants removed from protocol therapy for unacceptable adverse events will be following until resolution or stabilization of the adverse event.

**30-day post-drug visit:** A site visit is to be performed at 30 days ( $\pm 7$  days) after the last study drug is given, unless the subject is unable to travel due to deteriorating medical condition, due to the potential risk for delayed immune-related toxicities. The visit will include the safety procedures detailed below:

- Adverse event assessment.
- Symptom-directed physical exam and KPS assessment.
- Vital signs: weight, temperature, resting blood pressure, pulse and respiration rate.

CONFIDENTIAL

- Serum chemistry: sodium, potassium, chloride, bicarbonate, calcium, magnesium, phosphorous, glucose, albumin, creatinine, blood urea nitrogen (BUN), uric acid, ALT, AST, total bilirubin, direct and/or indirect bilirubin, alkaline phosphatase (ALP), and lactate dehydrogenase (LDH).
- Hematology: WBC count, 3-cell differential (ANC, monocyte count, lymphocyte count), hemoglobin, hematocrit, and platelet count.

**90-day post-drug safety follow-up:** An extended safety follow-up is to be performed at 90 days ( $\pm 14$  days) after the last study drug is given. This may be performed via documented phone conversation with a study nurse or clinician or physician.

**Extended follow-up post-treatment:** Subjects should be contacted every 3 months ( $\pm 14$  days) for survival status and initiation of any new anti-cancer treatments until death, withdrawal of permission to record at least survival data, or subject is lost to follow-up. Contact may include clinic visit, telephone contact, e-mail, mail or medical record review. The date of death, initiation of any new anti-cancer treatments and date of last contact should be documented.

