  23. Research Blood Samples: For all patients, whole blood will be drawn at two timepoints: C1D1 (pre-dose) and at C2D1. For subjects at NYULMC, four purple top EDTA tubes (40 mL) will be drawn, one EDTA tube will be sent to the CBRD and three EDTA tubes will be sent immediately to the IMC. For subjects at other sites: **\*Subsites should NOT schedule research blood draws on Fridays as the NYU CBRD will not be able to receive specimens on weekends.** 40 mL of blood will be drawn into two types of tubes: 10 mL will be drawn into one Cell-Free DNA BCT® collection tube and 30 mL will be drawn into three purple top EDTA (10 mL) tubes. Blood samples will be immediately shipped overnight to NYULMC per instructions in the **Lab Manual**.
  24. Optional tumor biopsy: If subjects undergo tumor resections or biopsies during the study period after treatment initiation, or after progression on HFRT + Avelumab, a tumor specimen will be collected for research purposes. For details see **Section 6.8.3** and **Attachment 7**.
  25. Monitored throughout the study via safety assessments, observation, and participant reporting.
  26. End of treatment assessments to be performed within 7 days after the last drug administration or within 7 days after decision to end treatment. After the end of treatment, each subject will be followed for 30 days for adverse event monitoring and 90 days for serious adverse event reporting. Assessments may continue for ongoing reportable adverse events. After coming off study, patients will be contacted every 3 months to assess survival status.
  27. A site visit is to be performed at 30 days ( $\pm 7$  days) after the last study drug is given, unless the subject is unable to travel due to deteriorating medical condition, due to the potential risk for delayed immune-related toxicities. All participants will be followed until resolution or stabilization of any serious or reportable adverse events occurring during treatment or starting within 30 days of last study drug.

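### Section 4.5.2 limits survival follow-up to non-progressors, against the rest of the protocol, and the 24-month study duration does not fit the plan's own treatment and follow-up periods

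*Combined protocol and SAP*

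**What the plan says.** **Restrictive wording.** Section 4.5.2: "Subjects who discontinue for reasons other than progressive disease will have post-treatment follow-up for survival". Section 5.2.3.7 has a patient who stops treatment but stays in the study either attend the remaining visits or "continue in the follow-up phase of the study until progression of disease or closure of the study", and cites 4.5.2 for this.

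**Inclusive wording.**
- Section 4.5.2, next sentence: "After coming off study, each subject will be contacted every 3 months by telephone or medical record review to assess survival status". The exits listed there are withdrawn permission, loss to follow-up and death.
- Section 3.1.2: "All subjects will be followed by telephone contact every 3 months or medical record review for overall survival until death".
- Section 6.8: contact every 3 months "for survival status and initiation of any new anti-cancer treatments until death, withdrawal of permission to record at least survival data", or until loss to follow-up.
- Attachment 1, footnote 26: "After coming off study, patients will be contacted every 3 months to assess survival status".

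**Endpoint and analysis.** Section 3.3 makes 12-month OS a secondary endpoint, and Section 7.1.1 sets a 25% one-year reference. Section 7.2.2 uses Kaplan-Meier with censoring at last follow-up. No OS data cut or minimum follow-up is given.

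**Duration.** The Study Summary gives "Approximately 24 months from start of screening to last subject processed and finishing the study". The same summary allows avelumab for up to 2 years per subject. No accrual rate appears anywhere.

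**The concern.** Sections 5.2 and 5.2.2 send every subject who stops therapy to 4.5.2, so four sites will read the restrictive sentence as an instruction. Section 3.1.2 expects about 4 months of participation, taken from the median PFS on standard therapy, so most subjects will probably stop because of progression. Those subjects are also the ones at highest risk of death. If their survival is not recorded after progression, the censoring is informative and the Kaplan-Meier estimate rises. The missing data may be hard to recover later.

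The duration raises a second, separate question: whether the plan leaves enough calendar time for the phase II patients to reach 12 months.

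**Working it through.** **1. Effect of censoring progressors.** The documents give no joint model for progression and death, so the inputs are assumptions: exponential PFS with median 4.5 months, 90% of PFS events being progression, a constant death hazard after progression, and median OS 9 months (the typical value cited in Section 7.1.1).

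- PFS hazard: λ = ln 2 / 4.5 = 0.154 per month.
- True OS(t) = e^(−λt) + 0.9λ(e^(−μt) − e^(−λt))/(λ − μ). Setting OS(9) = 0.50 gives μ = 0.205 per month.
- True OS(12) = 0.353, about 35%.
- All progressors censored at progression: only deaths without progression count, so the estimate tends to exp(−0.1 × 0.154 × 12) = exp(−0.185) = 83%.
- A random fraction q of progressors censored: weight the post-progression group by (1 − q) in the hazard and integrate to 12 months. This gives about 40% for q = 0.25 and 48% for q = 0.5.

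A simulation of the same model gave 36%, 83% and 41% for the true, all-censored and quarter-censored cases, which agrees within a point.

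Sensitivity, using the plan's own null PFS6 of 40% at 168 days (5.52 months) and its 25% one-year reference: λ = −ln(0.40)/5.52 = 0.166. With 5%, 10% or 20% of PFS events being deaths without progression, full censoring gives exp(−share × 0.166 × 12) = 90%, 82% or 67%, against a true 25%.

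**2. Duration against treatment and follow-up.** This needs no accrual rate. A subject who starts at any time after screening opens and takes the full 2 years finishes after month 24. The 90-day safety contact and survival contact until death come later still.

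**3. Duration against 12-month OS.** Inputs: 6 lead-in subjects and then a 28-day stop (Section 5.2.1); 18 subjects in stage 1 and 25 in stage 2 (Section 3.1.2); six months defined as six 28-day cycles (Section 7.2.2). Accrual at r per month is assumed, as is a pause for the stage 1 readout.

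- Fixed time: 28 days + 168 days + 12 months = 0.92 + 5.52 + 12 = 18.4 months.
- Left for accruing 6 + 18 + 25 = 49 subjects: 24 − 18.4 = 5.6 months, so r must be about 8.8 per month.
- If the 3-month iRANO confirmation of progression is also awaited, the required rate is 19.1 per month.

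| r per month | Last stage 2 patient reaches 12 months at month | Stage 2 patients with 12 months by month 24 |
|---|---|---|
| 2 | 42.9 | 0 of 25 |
| 3 | 34.8 | 0 of 25 |
| 4 | 30.7 | 0 of 25 |
| 5 | 28.2 | 3 of 25 |
| 6 | 26.6 | 9 of 25 |
| 8 | 24.6 | 20 of 25 |
| 9 | 23.9 | 25 of 25 |

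Without a pause, the last of the 43 reaches 12 months at 25.2 months if r = 4, and at 22.7 months if r = 5.

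**4. Cost of a cut at month 24.** The 95% half-width at 25% is 1.96 × √(0.25 × 0.75/n): about 13 points with n = 43 complete and 20 points with n = 18. The second figure is pessimistic, because partly followed stage 2 patients also contribute to the Kaplan-Meier estimate.

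**The case against.** The strongest reply is that the plan already follows everyone. Four places say so, and the exits listed in 4.5.2 do not include progression. Section 6.8 also collects new anti-cancer treatments, which fits contact after progression. Section 5.2.3.7 does not mention survival and reads most naturally as visit follow-up of patients who have not yet progressed. This largely stands: a reader might infer that survival follow-up of progressors is undecided or excluded by design, and the documents do not support that. It does not remove the defect, because the restrictive sentence sits in the section to which sites are directed.

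The 83% is a worst case in which every site censors every progressor. The quarter-censored case shifts the estimate by about 5 points, well inside the sampling error with 43 patients. That is fair, although the shift always goes in the favourable direction.

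On timing, a reader might infer that the study closes before stage 2 patients can reach 12 months, so that 12-month OS would be biased or unavailable. The documents do not establish this. They give no accrual rate and no closure rule, the pause before stage 2 is implied rather than written, and the 24 months is approximate. A calendar cut is administrative censoring, which Kaplan-Meier handles, and lead-in and stage 1 patients would still supply 12-month data.

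**Conclusion.** The wording conflict is real and should be corrected. It is a sentence to repair in a plan that otherwise follows all subjects for survival. If the restrictive reading were applied throughout, 12-month OS could read 83% against a true value of about 35%; with a quarter of progressors lost, it would read about 40%. Both figures rest on the stated assumptions.

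The 24-month duration is inconsistent with up to 2 years of treatment per subject and with follow-up until death. Its effect on 12-month OS is conditional: with a stage 1 pause, accrual of about 9 per month is needed for all stage 2 patients to reach 12 months by month 24. Falling short costs precision and does not itself bias the estimate. 12-month OS is secondary with no decision rule attached, and the primary PFS6 test is unaffected.

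**What to change.** 1. Reword Section 4.5.2 so that all treated subjects, whatever their reason for stopping and including progression, are followed every 3 months for survival until death, withdrawal of that permission or loss to follow-up.
2. Make Section 5.2.3.7 consistent, separating visit follow-up from survival follow-up.
3. Restate the study duration with its accrual assumption, and say whether accrual pauses for the stage 1 readout.
4. Set the 12-month OS data cut at 12 months after the last phase II subject's first dose, and state it in Section 7.2.2.

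The cost is a few sentences and a longer stated duration. The contact schedule already exists in Section 6.8, so no new procedure is added.

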#### CONFIDENTIAL

If a subject withdraws permission to record at least survival data after coming off treatment, this must be documented along with the date the subject withdraws permission. Subjects will be considered lost to follow up if no medical records are available to be reviewed and two phone calls each to the subject and then the subject's next-of-kin (if the subject does not respond) are not returned over two consecutive 3 month periods.

## 5 Study Drug

### 5.1 Description

Avelumab (company code: MSB0010718C) is a fully human antibody (calculated molecular weight of 143,832 Dalton) of the immunoglobulin G (IgG) 1 isotype that specifically targets and blocks PD-L1, the ligand for PD-1 and blocks the interaction between PD-L1 and PD-1. This removes the suppressive effects of PD-L1 on anti-tumor CD8+ T cells, resulting in the restoration of cytotoxic T cell response.

Avelumab drug product is a sterile, clear, and colorless concentrate for solution intended for intravenous (IV) infusion. The drug is presented at a concentration of 20 mg/mL in single-use glass vial containing 200 mg of Avelumab.

Avelumab drug product must be stored at 2°C to 8°C until use, and it must not be frozen. Rough shaking of avelumab product must be avoided. Avelumab drug product must be diluted with 0.9% saline solution; alternatively a 0.45% saline solution can be used if needed. It is recommended that the diluted avelumab solution is used immediately. Avelumab is administered as a 1-hour (-10/+20 minutes) IV infusion.

The **Pharmacy Manual** will be provided and contains specific instructions for Avelumab dose calculation, reconstitution, preparation of the infusion fluid, and administration.

### 5.2 Treatment Regimen

This is a multicenter, open-label, single-arm phase II trial of Avelumab in combination with hypofractionated radiation (HFRT) in adults with transformed *IDH* mutant GBM (for **Subject Selection Criteria** see **Section 4**; for **Study Schema**, see **Section 3.1.1**; for **Schedule of Events**, see **Attachment 1**; for details on **Radiation Treatment**, see **Attachment 6**).

An initial **Safety Lead-In** of 6 subjects will be conducted to define the safety and RP2D of Avelumab in combination with HFRT as detailed below in **Section 5.2.1**. The dose of Avelumab administered during the safety lead-in will initiate at the established phase II dose of Avelumab when administered as monotherapy (Dose Level 0). The safety lead-in also incorporates a de-escalation of Avelumab dosing if unexpected dose-limiting toxicity is observed in the first 6 subjects and follows a 3+3 phase I design as described below (**Section 5.2.1**). In the unlikely event that the Safety Lead-In phase of this study is unable to define an adequately safe dose of Avelumab administered with HFRT, the study will be stopped.

The RP2D of Avelumab administered with HFRT will be incorporated into the **Phase II portion** of this study.

**Avelumab** will be administered in an outpatient setting as an intravenous (IV) infusion; however, inpatient administration is permitted. Avelumab will be provided to patients enrolled on this study by EMD Serono/Merck KGaA.

**Pre-medication for Avelumab:** Subjects will receive Avelumab by IV infusion once every 2 weeks. Premedication with an antihistamine and with paracetamol (acetaminophen) (for example, 25-50 mg diphenhydramine and 500-650 mg paracetamol [acetaminophen] IV or oral equivalent) approximately 30 to 60 minutes prior to each dose of Avelumab is mandatory prior to the first 4 infusions. Premedication should be administered for subsequent avelumab infusions based upon

CONFIDENTIAL

This material is the property of the NYU School of Medicine and Langone Medical Center. Do not disclose or use except as authorized in writing by the study sponsor

clinical judgment and presence/severity of prior infusion reactions. This regimen may be modified based on local treatment standards and guidelines as appropriate provided it does not include systemic corticosteroids.

**Infusion:** Avelumab is administered as a 1-hour (-10/+20 minutes) IV infusion. Each patient's dose will depend on individual body weight. The dose of Avelumab must be adjusted each dose for changes in body weight of  $\geq 10\%$ . Dose adjustments for changes in body weight of  $< 10\%$  will be at the discretion of the investigator. Following all avelumab infusions, subjects must be observed for 30 minutes post-infusion for potential infusion-related reactions. The **Pharmacy Manual** contains specific instructions for Avelumab dose calculation, reconstitution, preparation of the infusion fluid, and administration.

**Setting:** Avelumab should be administered in a setting that allows for immediate access to an environment that can immediately administer therapy for anaphylaxis, such as the ability to implement immediate resuscitation measures. Steroids (dexamethasone 10 mg), epinephrine (1:1,000 dilution), allergy medications (IV antihistamines), bronchodilators, or equivalents, and oxygen should be available for immediate access.

Planned Avelumab regimens to be assigned may include:

- 1 mg/kg IV infusion every 14 days for 2 years
- 3 mg/kg IV infusion every 14 days for 2 years
- 10 mg/kg IV infusion every 14 days for 2 years

After screening procedures and registration, all subjects will be treated with one dose of Avelumab IV at the assigned dose level. Study treatment should begin as close as possible to the date on which the participant is registered. One treatment cycle is defined as 28 days, corresponding to 2 doses of Avelumab. Avelumab will be administered every 14 days after the first Avelumab dose up to 3 days before or after the scheduled Day ( $\pm 3$ ) of each drug administration due to administrative reasons (i.e., Days  $1 \pm 3$  and  $15 \pm 3$  of a 28-day cycle).

All subjects will receive **hypofractionated radiation (HFRT)** to a total dose of 25 Gy given as 5 Gy per fraction over 5 consecutive fractions (for details on Radiation Therapy administration see **Attachment 6**). HFRT must begin 1 week after the first dose of Avelumab (i.e., Day 8 of Cycle 1). HFRT should preferably be given on consecutive days (i.e., Day 8 to Day 12).

Every attempt must be made to obtain the original radiotherapy treatment plan in order to guide re-irradiation treatment planning

All subjects will be evaluated every 8 weeks with radiographic imaging to assess response to treatment. The **Immunotherapy Response Assessment for Neuro-Oncology (iRANO) criteria (Attachment 3)**, which is based on the immune-related response criteria and the RANO criteria for brain tumor response assessment, will be used as the primary efficacy endpoint of PFS6. Adverse events will be monitored throughout the trial and graded in severity according to the guidelines outlined in the NCI-CTCAE version 4.03.

Avelumab administration will continue for all subjects for 2 years or until the subject discontinues study therapy as per Subject Withdrawal guidelines, whichever comes first (**Section 4.5**). Subjects who are discontinued from study therapy will enter the post-study follow-up phase of the study as per **Section 4.5.2**.

The investigator shall take responsibility for and shall take all steps to maintain appropriate records and ensure appropriate supply, storage, handling, distribution and usage of trial treatments in accordance with the protocol and any applicable laws and regulations.

CONFIDENTIAL

This material is the property of the NYU School of Medicine and Langone Medical Center. Do not disclose or use except as authorized in writing by the study sponsor

